Patients with stroke resulting in hemiparesis and foot drop are affected by gait impairments such as poor symmetry, decreased velocity, and decreased endurance. AFOs have been shown to be an effective intervention for improving gait parameters in individuals who are in the chronic stage of stroke recovery (Tyson, Sadeghi-Demneh, & Nester, 2013; Tyson & Kent, 2013). Although, the majority of gait improvements occur within six months of stroke (Kwakkel, Kollen, & Lindeman, 2004), the effect of early bracing with different types of AFOs on gait outcomes has not been investigated thoroughly.

Purpose of the study:

The purpose of this study will be to identify whether patients in the subacute stage of stroke, who demonstrate foot drop, will have better gait outcomes when using a Double Adjustable AFO, or a Posterior Leaf Spring AFO. A secondary purpose will be to determine whether one week of practice significantly changes gait outcomes with either of the AFO conditions.

Research Hypotheses

The research hypotheses of this study are as follows:

1. There will be a difference in gait endurance measurements, gait symmetry measurements and gait velocity measurements at baseline when using custom Double Adjustable AFO compared to a PLS AFO in patients in subacute stage of stroke.
2. There will be a difference in gait endurance measurements, gait symmetry measurements and gait velocity measurements after one week of practice when using custom Double Adjustable AFO compared to a PLS AFO in patients in subacute stage of stroke.
3. After a week of practice, there will be a difference in gait endurance measurements, gait symmetry measurements and gait velocity measurements compared to baseline measurements, when using either custom Double Adjustable AFO or a PLS AFO in patients in subacute stage of stroke.

Significance of Study

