Reintegration to normal living is an ultimate goal of stroke rehabilitation. Difficulty in walking independently, especially outdoors, is reported as the most disabling consequence of stroke. (Pound, Gompertz, & Ebrahim, 1998). Even after rehabilitation, 63% of community dwelling stroke survivors reported dependency on others for community ambulation (Lord, McPherson, McNaughton, Rochester, & Weatherall, 2004). Gait velocity has been identified as a factor which predicts independent community ambulation in stroke survivors (Rosa, Marques, Demain, & Metcalf, 2014). Gait speed and gait endurance are also identified as predictors for community ambulation after stroke (Bijleveld-Uitman, van, & Kwakkel, 2013). Although my study is not looking at community ambulation specifically as an outcome, it is reasonable to assume that improvement in gait velocity and gait endurance with use of AFO will impact a stroke survivor's ability to improve participation in the community and to decrease caregiver dependency.

Methodology

Experimental design:

The research design for this experimental study will be a 2 factor within subject repeated measures 2x 2 design. The manipulated independent variables in the study will be 1) type of

AFO with two levels: (a) Double adjustable AFO and (b) Posterior leaf spring AFO and 2) Practice Time with 2 levels: (a) baseline, and (b) after 1 week of practice. The dependent variables in this study are the following: Gait endurance measured by 6 Minute Walk Test (6MWT), gait symmetry measured using GAITRite gait analysis system, and gait velocity measured using GAITRite gait analysis system.

Participants

Twenty participants over the age of 18, of any gender and ethnicity, diagnosed with first time unilateral stroke, 4 - 20 weeks post-stroke onset, resulting in hemiparesis with foot drop will be recruited. The number of participants was estimated based on previously reported studies. Hyun et al found significant differences in gait endurance measured by 6MWT when using AFO compared to using no AFO with 15 participants in a similar study (Hyun, Kim, Han, & Kim, 2014). In another study by Carse et al, gait velocity and gait symmetry were found to be significantly better with 8 participants (Carse, Bowers, Meadows, & Rowe, 2014). Therefore, for our study, the potential participant number was projected as 20.

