data including age, height, weight, leg length measurements on each side, and Fugl-Meyer Lower Extremity Assessment of sensorimotor function. Then the gait outcomes will be measured using one of the two AFO conditions in random order. Two possible orders will be written on piece of paper and an equal number of possible order selections will be put in a hat. The participant will select the order of AFO condition by drawing out of a hat. Randomization without replacement will be used. Once the order of AFO wearing has been determined, data will be collected in the randomly selected order. Participants will be allowed to use any type of assistive device of their choice, but the same device will be used for all conditions.

First, the 6MWT will be administered with the participant wearing the first randomized AFO. Participants will be asked to ambulate as far as possible in 6 minutes at a self-selected walking velocity through a well-lit indoor corridor. A five minute seated resting will be provided before the next measurement is taken. Next, gait symmetry and gait velocity measurements will be obtained using the GAITRite system. Participants will be given a practice trial walk prior to beginning of the testing. Participants will be asked to walk at their comfortable self-selected walking velocity along the walkway. They will begin walking three meters from the start of the walkway and will stop walking two meters past the end of the walkway. The beginning and end of the walking area will be marked with red tape for visibility. The verbal instruction will be “Please walk from this red line to that red line at your comfortable speed safely”. A second personnel will be walking close to the participant outside of the walkway to ensure safety. After a five minute sitting break, participant will be asked to walk as fast as they can safely. The verbal instruction will be “Please walk from this red line to that red line as fast as you can safely”. The GAITRite system will be able to capture both gait symmetry and gait velocity measurements with the same walk. Three trials will be performed of the self-selected velocity walk and fast

paced velocity walk. The calculated mean of the three trials will be used for data analysis. After a 10 minute seated rest break, the second AFO condition will be used and measurements will be repeated in the same order described above.

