To assess the effects of practice on the gait measures, AFO's will be randomized for practice. Participants will be randomized for which AFO they will wear first (the PLS or the DA AFO), by drawing out of a hat. Again randomization without replacement technique will be used. Then the participant will be provided with the selected type of AFO to practice with for the following week using a prescribed wearing schedule. At the end of the one-week practice time, the primary investigator will obtain the same measurements obtained at baseline with the participant wearing the type of AFO that was used to practice the week before. The same testing conditions and order of testing that were used at baseline will be employed. Once measurements are completed, the participant will be provided with the second type of AFO and will be asked to wear for one week using the same prescribed wearing schedule as before. Final measurements will be taken after completion of the one-week practice using the second type of AFO with the same testing conditions and orders. At the conclusion of testing each participant will be asked which AFO they will prefer to use for their daily ambulatory needs for descriptive analysis. All data collected will be de-identified and stored in the Primary Investigator's secure personal computer. Any documents used such as Participant information sheet will be securely locked in a cabinet at Texas Woman's University where only the Primary investigator will have access.

Data Analysis

The following statistics will be calculated using SPSS for Windows. Descriptive statistics will be calculated for all demographic data including age, height, weight, time since onset Fugl Meyer lower extremity assessment score and AFO preference.

Differences in gait endurance will be analyzed using a 2x2 repeated measures ANOVA. Differences in gait symmetry, and gait velocity between the two AFO conditions and two practice conditions will be analyzed using two separate 2x2 repeated measures MANOVA. If assumption of sphericity is not met, Greenhouse-Geisser statistic will be used. An alpha level of .05 will be used to determine significance of differences, with a Bonferroni correction applied as needed to protect against Type I error.

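### The randomised day-1 AFO test order is missing from the planned models, so a first-versus-second position effect would cost power on hypothesis 1 and, if the analysed orders are unequal, shift the estimate

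*Combined protocol and SAP*

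**What the plan says.** All references are to the combined protocol and SAP.

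- **Research Hypotheses.** The first hypothesis is non-directional and compares the two AFOs on day 1: "There will be a difference in gait endurance measurements, gait symmetry measurements and gait velocity measurements at baseline".
- **Procedures.** Both AFOs are tested in one session. Equal numbers of slips for the two orders go into a hat and are drawn without replacement; the total number of slips is not given. Then: "Once the order of AFO wearing has been determined, data will be collected in the randomly selected order". Each AFO gets a 6MWT, a practice walk, three comfortable passes and three fast passes. "After a 10 minute seated rest break, the second AFO condition will be used", and the battery is repeated.
- **Experimental design.** The study is a "2 factor within subject repeated measures 2x 2 design"; the factors are AFO type and practice time.
- **Data Analysis.** "Differences in gait endurance will be analyzed using a 2x2 repeated measures ANOVA". Symmetry and velocity differences "between the two AFO conditions and two practice conditions will be analyzed using two separate 2x2 repeated measures MANOVA". No order, sequence or position term appears, and no check for an order effect.
- **Participants.** "Therefore, for our study, the potential participant number was projected as 20".

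Procedures also keeps the testing order the same at later visits. That governs how the sessions are run; it does not put order into a model.

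**The concern.** The second AFO is tested after a full walking battery in the first, in people 4 to 20 weeks after stroke, some of whom need contact guard assistance. Fatigue could lower second-position results and familiarisation could raise them. By randomising the order, the protocol itself treats position as a possible nuisance.

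If second position shifts performance by p, a participant's DA minus PLS difference carries −p when DA goes first and +p when PLS goes first. That variation is known for every participant, yet the planned models would count it as unexplained error. Hypothesis 1 rests on this single session, and the sample size was set without a stated effect size, SD or power, so there is no documented margin to absorb avoidable error.

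The practice-order draw is a separate draw, so modelling that order would not remove the day-1 position effect.

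**Working it through.** **The plan's own figure.** The 20 participants were projected from earlier studies of 15 and 8. With no effect size, SD or power stated, the figure cannot be reproduced. As a reference point, a two-sided paired t test with n = 20 and alpha .05 ("An alpha level of .05 will be used to determine significance of differences") has 80% power at a true effect of 0.66 SD of the paired difference (noncentral t, 19 df).

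**Model.** Let D be a participant's baseline DA minus PLS difference, τ the true AFO effect and p the second-minus-first position effect. Then D = τ − p + e if DA is first and D = τ + p + e if PLS is first. The within-order SD of D is set to 1. Both p and τ are assumptions.

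**Without an order term**

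- Bias = p(n_PLS-first − n_DA-first)/n.
- Expected sample variance of D = 1 + p² × 4n₁n₂/[n(n − 1)].

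At 10:10 the bias is 0 and the variance is 1 + p² × 400/380 = 1 + p² × 20/19. Given a 10:10 split, the estimate itself is no more variable than before; its estimated standard error is too large, which makes the test conservative.

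**With an order term**

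- The estimate is the unweighted mean of the two order-specific mean differences.
- SE = ½√(1/n₁ + 1/n₂), with n − 2 df.

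Results at 10:10, n = 20, τ = 0.66 (simulation of 100,000 trials per case, checked by numerical integration):

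| p (SD) | SE factor, no term | Power, no term | Power, with term | Type I error, no term |
|---|---|---|---|---|
| 0 | 1.00 | 80% | 79.8% | 5.0% |
| 0.25 | 1.03 | 78% | 79.8% | 4.4% |
| 0.5 | 1.12 | 72% | 79.8% | 2.9% |
| 1.0 | 1.43 | 49% | 79.8% | 0.6% |

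**Unequal orders.** If the hat holds 20 slips, neither order can exceed 10. The chance of each split below assumes such a hat and losses unrelated to order.

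| Split | Size of bias | At p = 0.5 | Chance of this split |
|---|---|---|---|
| 10:8 | 2/18 = 0.11p | 0.06 SD | 2 × 45/190 = 47% |
| 10:7 | 3/17 = 0.18p | 0.09 SD | 2 × 120/1140 = 21% |
| 10:6 | 4/16 = 0.25p | 0.125 SD | 2 × 210/4845 = 8.7% |

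The sign of the bias depends on which order is larger. At 10:6 and p = 0.5, unadjusted power is 42% when the bias opposes the effect and 77% when it favours it. With the order term it is 66% either way.

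**Cost of the term when p = 0.** At 10:10, power goes from 80.0% to 79.8%. At 10:7 the SE rises from 1/√17 = 0.243 to ½√(1/10 + 1/7) = 0.246, about 2 power points with the lost df. At 10:6 it rises from 0.250 to 0.258, about 3 points.

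**The case against.** The strongest reply is that the design already deals with position. An equal-slip draw without replacement gives exactly 10:10 if the hat holds 20 slips and all 20 participants are analysed, and averaged over random draws the contrast is unbiased at any size. This stands: leaving out the order term does not invalidate the test.

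Three stronger readings are tempting, and the documents do not support them.

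- *The false-positive rate rises.* At 10:10 it falls. At 10:7 it is about 4.7%, 4% and 2% for p = 0.25, 0.5 and 1.0, because the overstated standard error offsets the bias. At 10:6 it is still no more than 5%. It takes a split such as 10:5 to exceed 5% (6.2% at p = 0.5), and from a 20-slip hat that has probability 2 × 252/15504 = 3.3%.
- *The hypothesis 1 estimate is biased as planned.* It is biased only if the analysed orders are unequal, through losses, early stopping or a hat with more than 20 slips. At 10:7 and p = 0.5 the bias is 0.09 SD, about a third of the standard error.
- *Power will be badly hurt.* The 49% figure needs a position effect larger than the assumed AFO effect. Fatigue and familiarisation pull in opposite directions, and the seated rests and practice walk should limit both, so the net p may be near zero.

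Two further limits stand. The figures are for a paired comparison of day-1 values at alpha .05, not for the planned MANOVAs or a Bonferroni-corrected level. In the AFO main effect of the 2x2 model, baseline supplies half the contrast, so p enters halved. The order term also removes only the shared position effect; person-to-person variation in fatigue stays in the error.

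What the reply does not answer is why an order that was randomised and is known should be left in the error term.

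**Conclusion.** The point holds as a conditional loss of efficiency. The day-1 order is randomised but not modelled, so any shared position effect enters the error of the baseline AFO contrast. With 10:10 orders the analysis is valid and conservative. The power loss is about 2 points at p = 0.25 and about 8 at p = 0.5; the loss of about 31 points at p = 1.0 is an extreme case. With unequal orders there is also a shift of p(n₁ − n₂)/n.

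All of this rests on an assumed p, an assumed effect of 0.66 SD and a paired analysis at alpha .05, since the documents give no SD, effect size or position effect. It is not evidence that the planned test is invalid or that its false-positive rate is raised. The change is still worth making, because the trial is small, hypothesis 1 depends on one session and the information is already to hand.

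**What to change.** In Data Analysis, state that the baseline DA-versus-PLS contrast for 6MWT, velocity and symmetry includes the day-1 test order as a two-level between-subject factor (equivalently, session position as a fixed effect). Report the AFO estimate as the unweighted mean of the two order-specific mean differences with its 95% CI, and give the number analysed in each order. Enter the same factor wherever baseline values are used in the 2x2 models.

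The cost is one sentence, one factor in SPSS and one degree of freedom. No procedure or visit changes, and the order is determined for every participant on day 1. The change is not entirely free: if there is no position effect, it gives up about 0.2 power points at 10:10, about 2 at 10:7 and about 3 at 10:6.

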a) Gait endurance will be measured using the Six Minute Walk Test (6MWT).

Participants will be asked to ambulate as far as possible in 6 minutes at a self-selected walking velocity through a well-lit indoor corridor. Participants will be informed when half of the time is over, otherwise no verbal cueing or encouragement will be provided. A gait belt will be used to ensure patient safety. If the participant needs to sit during the testing, that will be allowed.

However the timer will not be stopped for sitting rest breaks. The primary investigator will walk beside the patient, without influencing the speed of ambulation to ensure safety. The distance ambulated during the six minutes will be measured in feet using a measuring wheel and then converted to meters for data analysis.

b) Gait Symmetry will be measured using the temporospatial measurements from the GAITRite™ (CIR systems, Havertown, PA, USA) computerized gait analysis system. The GAITRite walking system used in this study is a 16 feet long x 3 feet wide portable walkway with embedded pressure sensors at 1.27 cm intervals along the length of the walkway. As the participant ambulates on the walkway, the pressure of the foot activates the sensors that record the person's steps. The data will be sampled at 1000 Hz. These measurements are then sent to a computer program that analyzes the specified temporal spatial parameters using the algorithm built into the special software. This data can be saved and exported to Microsoft Excel where the data can be further analyzed (*GAITRite electronic walkway technical reference, revision L. 2013.*) Step symmetry will be calculated using the ratio of the affected step length to the unaffected step length during self-selected velocity walk and fast paced velocity walk, with perfect symmetry defined as 1.0.

c) Gait velocity in cm/sec will also be assessed using the temporospatial measurements of the self-selected pace walk and fast paced walk from the GAITRite™ computerized gait analysis system.

Procedures:

All measurements will be obtained from each participant during three testing sessions and by only one researcher to avoid inter tester reliability issues. On the first measurement day, participants receive their custom DA AFO. The primary investigator will collect demographic

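### The average effect of one week of AFO practice cannot be separated from recovery and repeat testing, and for the AFO worn second the change spans two weeks

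*Combined protocol and SAP*

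**What the plan says.** The section on the purpose of the study states the aim: "A secondary purpose will be to determine whether one week of practice significantly changes gait outcomes with either of the AFO conditions". Hypothesis 3 is worded more loosely: "After a week of practice, there will be a difference in gait endurance measurements", and likewise in symmetry and velocity, relative to baseline, with either AFO. Under Experimental design the second factor is "Practice Time with 2 levels: (a) baseline, and (b) after 1 week of practice".

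The Procedures section sets the timetable:

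- "All measurements will be obtained from each participant during three testing sessions".
- Day one: the full battery is run in one AFO and then, after a 10-minute seated rest, "the second AFO condition will be used and measurements will be repeated in the same order described above". Both AFOs therefore have an unpractised baseline.
- The practice phase is introduced with the aim "To assess the effects of practice on the gait measures". The order of wearing is drawn from a hat. After the first week "the primary investigator will obtain the same measurements obtained at baseline with the participant wearing the type of AFO that was used to practice". The other AFO is not tested at that visit.
- The second AFO is then worn for a week: "Final measurements will be taken after completion of the one-week practice using the second type of AFO with the same testing conditions and orders".

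The Data Analysis section plans a 2x2 repeated measures ANOVA for endurance and two 2x2 repeated measures MANOVAs for symmetry and velocity. It names no term for period or practice order. Participants are 4 to 20 weeks after stroke, and the Introduction cites reports that most gait improvement falls within the first six months.

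**The concern.** In each participant all unpractised values date from day one and all practised values come later. No repeat baseline, concurrent unpractised test or no-practice group is described. Practice is therefore tied to elapsed time and to repeat testing, in the very window that the protocol identifies as the one of greatest recovery.

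The label on the second factor level is also wrong for one of the two AFOs. For the AFO worn second, the interval from its baseline is two weeks, the first of them spent in the other device, and no washout is stated.

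At stake is the conclusion of the secondary purpose. A significant Practice Time effect would naturally be reported as a benefit of a week of practice, when recovery or familiarity with the tests could produce the same result.

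**Working it through.** The plan gives no figure to reproduce here. The 20 participants are projected from earlier studies of 15 and 8, with no effect size, SD or power.

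**Inputs.** From Procedures: three sessions (day one, end of week 1, end of week 2), both AFOs at session 1, one AFO at each later session, randomised practice order. From Participants and Data Analysis: n = 20, alpha .05. Assumed: a two-sided test, a 10:10 split of practice orders, and everyone completes.

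**1. Mean change from baseline.** Let pD and pP be the practice effects of the Double Adjustable (DA) and Posterior Leaf Spring (PLS) AFOs. Let r1 be recovery plus retest gain up to week 1, and r2 the same from week 1 to week 2. Let cDP be carryover from a DA week to the later PLS test, and cPD the reverse.

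| Practice order | Change in DA | Change in PLS |
|---|---|---|
| DA first | pD + r1 | pP + r1 + r2 + cDP |
| PLS first | pD + r1 + r2 + cPD | pP + r1 |

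**2. Identifiability.** There are four means and six unknowns (rank 4). Add any constant to both pD and pP and subtract it from r1: all four means stay the same. This holds even with both carryovers set to zero, so adding a practice-order term to the model would not identify the average practice effect. It becomes estimable only if recovery is linear (r1 = r2), carryover is zero and there is no retest gain. Allowing one common retest step makes it non-estimable again.

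**3. What the planned contrast estimates.** Averaging the four cells gives (pD + pP)/2 + r1 + r2/2 + (cDP + cPD)/4. With steady recovery g per week, mean practice effect p and mean carryover c, this is p + 1.5g + c/2 plus a retest term. The 1.5 arises because each person has one practised value at week 1 and one at week 2: (1 + 2)/2 = 1.5.

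**4. The retest term.** Session 1 has two batteries; sessions 2 and 3 have one each.
- A one-off gain R that appears only from session 2 adds R.
- If it is already present at the second battery on day one, the baseline mean contains R/2 and the contrast carries R/2.
- If that second battery is instead lowered by fatigue f, the baseline mean falls by f/2 and the contrast rises by f/2.

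**5. Illustration, 6MWT only.** Set practice, retest and carryover to zero. Express g in SDs of the participant-level contrast. The noncentrality is 1.5g × √20, with 19 df:

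| Assumed g (SD per week) | Noncentrality | Chance of p < .05 |
|---|---|---|
| 0.05 | 0.335 | 6.2% |
| 0.1 | 0.671 | 9.8% |
| 0.2 | 1.342 | 24.7% |
| 0.3 | 2.012 | 48.0% |
| 0.5 | 3.354 | 88.9% |

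If every interval were exactly one week, the rates at g = 0.1, 0.2, 0.3 and 0.5 would still be 7.1%, 13.6%, 24.7% and 56.5%. The two-week interval worsens the problem but does not create it.

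**6. What remains estimable.** At session 2 nobody has yet practised in the other AFO. The DA-first change minus the PLS-first change is (pD + r1) − (pP + r1) = pD − pP, provided that recovery and retest gain are equal in both AFOs.

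**7. The between-AFO comparison.** With 10:10 orders each AFO's practised mean carries 1.5g, so common drift cancels. With 12:8 completers the two means carry (12×1 + 8×2)/20 = 1.4g and (12×2 + 8×1)/20 = 1.6g, a difference of 0.2g.

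**The case against.** The strongest reply has four parts.

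- *Practice order is randomised.* This protects the comparison of the two AFOs from common drift. It does nothing for a before-after contrast, because both orders shift by the same 1.5g.
- *Hypothesis 3 asks only for a difference from baseline.* This stands. A reader might infer that hypothesis 3 is untestable; as worded it can be tested. The problem lies in the secondary purpose, in the stated aim of the practice phase, and in reading hypothesis 3 as an effect of practice.
- *Not every practice question is lost.* This also stands. A reader might infer that no practice claim of any kind is possible. Step 6 shows that the DA-minus-PLS difference in practice effect can be estimated from session 2, under a stated assumption.
- *The bias may be small, or even zero.* The documents give no weekly recovery rate, SD or retest gain, so nothing anchors the assumed range of g, and 6% to 89% runs from negligible to near-certain. Symmetry is a ratio with 1.0 as perfect; recovery could raise it in some people and lower it in others, so mean drift might cancel. The rates are also univariate, whereas symmetry and velocity are to be analysed by MANOVA. All of this limits what can be said about size. It does not restore identifiability: if recovery were negligible, this design could not show it.

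**Conclusion.** The point holds for the average practice effect. That this effect is not identifiable follows from the timetable alone and needs no assumption about recovery. The 1.5-week figure assumes balanced practice orders and steady recovery. The size and sign of the bias are unknown and may differ between outcomes, so the rejection rates are illustrations and not estimates.

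A reader might go further and conclude that the comparison of the two AFOs is invalid. The documents do not support that. Hypothesis 1 rests on day-one data and is unaffected. Hypothesis 2 is protected from common drift on average by the randomised practice order. That protection does not extend to unequal carryover, which would shift the practised DA-minus-PLS difference by (cPD − cDP)/2, but the documents give no ground for assuming such an inequality. The issue should be fixed, but it concerns how a secondary aim is interpreted, not the primary purpose.

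**What to change.** 1. Restate the secondary purpose, and hypothesis 3 to match, as change from baseline to the end of the practice period. Say that this combines practice, recovery and repeat testing, and note that session 1 has two batteries and later sessions one.
2. Report the change by AFO and by practice order (one week if worn first, two weeks if worn second) with 95% confidence intervals. Add the one-week and two-week changes pooled over AFOs.
3. Make no claim that practice caused the average change. If a practice claim is wanted, estimate the DA-minus-PLS difference by comparing session 2 changes from baseline between the two randomised practice orders. State the assumption that recovery and retest gain are equal in both AFOs.

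The cost is wording and reporting only, with no new visits or data. The price is a weaker secondary conclusion and limited precision. The 95% half-width is 2.093/√20 = 0.47 SD of the change for a pooled change at n = 20, and 2.262/√10 = 0.72 SD in an AFO-by-order cell of about 10. For the session 2 comparison of about 10 against 10 it is 2.101 × √(2/10) = 0.94 SD, so that contrast would be exploratory.
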